#### **5.5.1.8 DoR, DCR and PFS by IRC – RECIST**

Intracranial PFS, DoR, and DCR, as determined by the IRC according to RECIST v1.1, will be analyzed using the same methods described for intracranial PFS, DoR, and DCR determined by investigator on all patients who received at least one dose of study medication (safety evaluable population).

## 5.6 SAFETY ANALYSES

Safety analyses will be performed on the safety evaluable population.

In addition, patients in Cohort 2 will receive cobimetinib and vemurafenib during the run-in period (Cycle 1) and the triplet combination (cobimetinib, atezolizumab and vemurafenib) from Cycle 2 onwards. For the purpose of safety analyses in Cohort 2, the patients will be grouped according to whether they have received the triplet combination:

- cobimetinib+vemurafenib (Patients who discontinued therapy prior to any atezolizumab administration): patients who received any amount of cobimetinib and/or vemurafenib without any amount of atezolizumab
- atezolizumab+cobimetinib+vemurafenib: patients who received any amount of atezolizumab in addition to cobimetinib+vemurafenib.

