Based on data from the preceding cohorts, treatment in the fourth escalation cohort and expansion cohorts has been established as an initial 28-day run-in with 21 days 960 mg vemurafenib twice daily (BID) then seven days 720 mg vemurafenib BID plus 60 mg cobimetinib once daily (QD) Days 1-21. Following completion of the 28-day run-in, atezolizumab is added to the combination for a final regimen of 60 mg cobimetinib QD (21 days on, 7 days off each cycle) plus 800 mg atezolizumab every two weeks (Q2W) plus 720 mg vemurafenib BID (Days 1-28 of each cycle).

As of the January 17, 2017 clinical cut-off date, 38 patients had received combination treatment with cobimetinib, atezolizumab and vemurafenib and the median survival follow-up was 10.1 months (95% confidence interval [CI]: 8.6, 11.0). Approximately two-thirds (25/38 or 65.8%) of the efficacy-evaluable patients had a confirmed response as assessed by the investigator per RECIST v1.1, with the majority (19/25) as partial responders. The median duration of response (DOR) could not yet be estimated based on only 28.0% of patients reporting a PFS event.

Thirty-nine patients receiving the triplet regimen were evaluable for safety at the clinical cut-off. Thirty-eight of these patients reported an adverse event. The most common adverse events ($\geq 20\%$) following completion of the run-in period included diarrhoea (59%), nausea and arthralgia (56.4% each), pyrexia (53.8%), photosensitivity reaction and fatigue (48.7% each), AST increased (46.2%), pruritus and alanine aminotransferase (ALT) increased (38.5% each), oedema peripheral (35.9%), constipation and hypertension (33.3% each), vomiting, influenza-like illness and cough (30.8% each), chills, rash maculopapular and anaemia (28.2% each), decreased appetite (25.6%), myalgia and back pain (23.1% each), and dry skin, blood creatinine increased, hypophosphatemia and headache (20.5% each).

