### 5.6.2 Adverse Events

Verbatim description of AEs will be mapped to Medical Dictionary for Regulatory Activities (MedDRA) thesaurus levels and graded according to the National Cancer Institute Common Terminology Criteria for Adverse Events (NCI CTCAE) Version 4.0. AEs that occur during or after the first dose of study treatment (i.e., treatment-emergent adverse events [TEAEs]) will be included in the summary tables.

Adverse events will be summarized by MedDRA term, appropriate MedDRA levels (System Organ Class [SOC] and Preferred Term [PT]), and when specified by NCI CTCAE grade. For each patient, multiple occurrences of the same event will be counted once at the maximum severity.

The following adverse events will be summarized by SOC or medical concept for AEs of special interest (AESIs), PT, and NCI CTCAE grade, for each cohort:

- Adverse events (AEs)
- AEs and AESIs of Grade 3 or higher
- Adverse events related to i) any study treatment, ii) atezolizumab, iii) cobimetinib, iv) vemurafenib (Cohort 2 only), v) all study treatment.

- SAEs
- AESIs

The following AEs will be summarized by SOC or medical concept for AESIs and PT for each cohort:

- AEs
- SAEs
- AEs and SAEs related to i) any study treatment, ii) atezolizumab, iii) cobimetinib, iv) vemurafenib (Cohort 2 only), v) all study treatment.
- Adverse events leading to discontinuation of i) any study treatment, ii) atezolizumab, iii) cobimetinib, iv) vemurafenib (Cohort 2 only), v) all study treatment.
- Adverse events leading to dose modification or interruption of i) any study treatment, ii) atezolizumab, iii) cobimetinib, iv) vemurafenib (Cohort 2 only), v) all study treatment.
- AESIs specific to i) atezolizumab, ii) cobimetinib+vemurafenib, iii) the combination, based on lists of pre-defined terms.
- AESIs leading to discontinuation of i) atezolizumab, ii) cobimetinib, iii) vemurafenib
- AESIs leading to dose modification or interruption of i) atezolizumab, ii) cobimetinib, iii) vemurafenib
- Fatal AEs
- Serious AESIs

Adverse events will be summarized by PT for each cohort. In addition, deaths, SAEs, AESIs, and AEs during the run-in period and the triple combination period (i.e., post run-in), will be summarized for Cohort 2 only.

All listings of AEs will include all AEs. AEs associated with coronavirus disease (COVID-19) will be listed.

All deaths and causes of death will be summarized by cohort.

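### Cohort 2 safety columns split by ever/never atezolizumab put run-in events in the triplet column, and the planned period summaries only partly correct this

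*SAP*

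**What the plan says.** Protocol 4.3.2.2 gives Cohort 2 a run-in cycle of vemurafenib and cobimetinib and adds atezolizumab from Cycle 2. Protocol 5.1.6.2 allows the run-in to extend from 28 to 56 days.

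SAP 5.6 performs safety analyses on the safety-evaluable population and adds, for Cohort 2, that "the patients will be grouped according to whether they have received the triplet combination". The doublet group is described as "Patients who discontinued therapy prior to any atezolizumab administration". The triplet group is "patients who received any amount of atezolizumab in addition to cobimetinib+vemurafenib".

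SAP 5.6.2 sets the counting window: "AEs that occur during or after the first dose of study treatment (i.e., treatment-emergent adverse events [TEAEs]) will be included in the summary tables". For each patient, "multiple occurrences of the same event will be counted once at the maximum severity".

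The same section also plans a split by period. Deaths, SAEs, AESIs and "AEs during the run-in period and the triple combination period (i.e., post run-in), will be summarized for Cohort 2 only". The SAP amendment rationale gives the purpose of that split as looking at safety in the triplet period and in the doublet-only period.

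**The concern.** The column a patient goes into depends on something that happens after treatment starts, namely reaching atezolizumab. The event window opens before that. This has two consequences in any table with ever/never columns.

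- A patient who later receives atezolizumab brings all Cycle 1 events into the triplet column, although none of them arose on the triplet.
- The doublet column is not a sample of doublet experience. It contains only patients who stopped before atezolizumab, while every triplet patient got through the run-in.

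The period summaries are the natural remedy, but they cover only some AE categories and their rules are incomplete. The study has no hypothesis test, so these descriptive tables are its safety result for the cohort that stayed open to enrolment. A reader who takes the triplet column as toxicity on atezolizumab, or the doublet column as a reference, would be misled.

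**Working it through.** The plan states no figure on this point, so there is nothing to reproduce. The check sets the rules side by side and then illustrates their size. All rates, durations and shares below are assumptions unless a source is given.

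**1. Rules combined.** The group is ever/never atezolizumab (SAP 5.6). The window runs from the first dose of study treatment (SAP 5.6.2). The first dose in Cohort 2 is a run-in dose without atezolizumab (Protocol 4.3.2.2). Run-in events of triplet patients therefore count in the triplet column.

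**2. Size of the carry-over.** Let a be the run-in incidence among patients who go on to atezolizumab and b their post-run-in incidence, taken as independent. Whole-window incidence is 1 − (1 − a)(1 − b), and the excess over b is a(1 − b).

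- a = 20%, b = 40%: 1 − 0.80 × 0.60 = 52%, an excess of 12 points.
- Smallest excess in the range tried, a = 10%, b = 56.4%: 0.10 × 0.436 = 4.4 points.
- Largest, a = 40%, b = 20%: 0.40 × 0.80 = 32 points.

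The upper value of b equals the 22/39 = 56.4% with Grade 3/4 events in Study GP28384 (Protocol 1.3.2.3). It is used only to set a range.

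**3. Size of the doublet column.** Planned Cohort 2 enrolment is about 60 (Protocol 3.1). The share never reaching atezolizumab is not given; 5% to 15% is assumed.

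| Share | Doublet n | Triplet n | Example in doublet column | Exact 95% CI |
|---|---|---|---|---|
| 5% | 3 | 57 | 1/3 | 0.8% to 90.6% |
| 10% | 6 | 54 | 3/6 | 11.8% to 88.2% |
| 15% | 9 | 51 | 4/9 | 13.7% to 78.8% |

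**4. What the period summaries leave open.**

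- *Categories.* No period split is stated for Grade 3 or higher AEs, treatment-related AEs, or AEs leading to discontinuation or to dose modification or interruption.
- *Boundary.* The second period is defined as post run-in. The SAP does not say whether that means Day 28, Cycle 2 Day 1 or the first atezolizumab dose, and the run-in can last 56 days. AEs are collected to 30 days after the last dose, and SAEs and AESIs to 90 days, or until new systemic anti-cancer therapy if sooner (Protocol 5.3.1). A run-in-only patient could thus have an event tabulated in the triple-combination period without having had atezolizumab.
- *Denominator.* None is given for either period.
- *Worsening events.* There is no rule for an event that starts in run-in and worsens later.
- *Time.* Exposure is summarized by cohort and drug (SAP 5.6.1), not by period.

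**5. Effect of unequal period length.** Crude incidence under a constant first-event hazard λ is 1 − exp(−λt), with t = 28/30.44 = 0.92 months for the run-in and assumed triplet durations of 4, 8 and 12 months.

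| λ per month | 28 days | 4 months | 8 months | 12 months |
|---|---|---|---|---|
| 0.05 | 4.5% | 18.1% | 33.0% | 45.1% |
| 0.10 | 8.8% | 33.0% | 55.1% | 69.9% |
| 0.20 | 16.8% | 55.1% | 79.8% | 90.9% |

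At λ = 0.10 the ratio to the run-in is 33.0/8.8 = 3.8 to 69.9/8.8 = 7.9 with no change in rate. With a 56-day run-in (t = 1.84 months) the run-in figure is 16.8%, and the ratios are 33.0/16.8 = 2.0 to 69.9/16.8 = 4.2.

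**The case against.** The strongest reply is that the plan already separates the periods. A reader might infer from the column definitions that run-in toxicity is reported only as triplet toxicity. The documents do not support that: SAP 5.6.2 prespecifies run-in and post-run-in summaries of deaths, SAEs, AESIs and AEs. Nor does it follow that nothing will be comparable with Study GP28384. Protocol 1.3.2.3 reports that study's common AEs after completion of the run-in, and the post-run-in AE summary follows the same convention. Only the whole-window columns differ.

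A second reply is that no comparison is intended. SAP section 2 makes every analysis descriptive, and the doublet column is openly labelled as patients who stopped before atezolizumab. A reader might infer that the plan means to isolate the effect of adding atezolizumab; it does not say so. An all-treated Cohort 2 display is arguably planned too, since the grouping is introduced as an addition.

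A third reply is that exposure-adjusted rates would not isolate atezolizumab either. Under Protocol 4.3.2.2 vemurafenib is 960 mg BID on Days 1–21 of run-in and 720 mg BID thereafter, so dose and period are confounded. This is right and limits what the fix can claim.

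A fourth concerns data. Protocol 5.3.5.4 has the eCRF record a persistent event's initial and most extreme severity, and asks for a date only when the event becomes serious. The documents do not show that grade-change dates are collected, so counting later worsening may not be possible.

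These replies narrow the point. They do not supply the missing AE categories, the boundary, the denominators or the adjustment for time, and they do not change what the triplet column contains.

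**Conclusion.** The point holds in limited form and should be fixed. In tables with ever/never-atezolizumab columns, the triplet column includes pre-atezolizumab events and the doublet column contains only early stoppers. This follows from the text and needs no assumption. The SAP does not say which of its by-cohort tables carry these columns, so how many are affected is unknown.

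The period summaries offset the problem for overall AEs, SAEs, AESIs and deaths, but not for the other AE categories, and their boundary, denominator and time at risk are undefined. The carry-over of about 4 to 32 points rests on assumed, independent incidences. The 4- to 8-fold ratio between periods (2- to 4-fold for a 56-day run-in) rests on an assumed hazard of 0.10 per month and assumed durations. Both show how the tables behave and do not predict results. No efficacy result or hypothesis test is affected.

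**What to change.** In SAP 5.6 and 5.6.2:

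- **Triplet-period tables:** count events with onset on or after the first atezolizumab dose. The denominator is Cohort 2 patients with at least one atezolizumab dose.
- **Run-in tables:** count events before the first atezolizumab dose, or to the end of AE reporting if it was never given. The denominator is all treated Cohort 2 patients.
- **Categories:** extend both sets to Grade 3 or higher AEs, treatment-related AEs, and AEs leading to discontinuation or to dose modification or interruption.
- **Time at risk:** add exposure-adjusted first-event rates for each period, such as first events per 100 patient-months. State that they are descriptive and do not isolate atezolizumab, because the vemurafenib dose also changes between periods.
- **Columns:** keep an all-treated Cohort 2 column. Label any ever/never-atezolizumab columns as whole-study and not for comparison.
- **Worsening:** count a grade increase after the first atezolizumab dose only if grade-change dates are collected; otherwise use onset alone and say so.

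The change is to SAP wording and table shells. Onset-based tables should need no new data. The cost is more tables, and period tables that do not sum to whole-study incidence, which the all-treated column still gives.

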### 5.6.1 Extent of Exposure

Study drug (atezolizumab, cobimetinib, and vemurafenib) exposure will be summarized for each cohort using descriptive statistics.

The overall number of cycles initiated (i.e., for drug combination) and the overall duration of treatment (in months) will be provided.

For each study drug separately, the total number of cycles initiated, the duration of treatment (in months), the duration categories in months, the cumulative dose, the dose intensity (%), the number of dose modification during the study and the reason for dose modification will be summarized.

### 5.6.2 Adverse Events

Verbatim description of AEs will be mapped to Medical Dictionary for Regulatory Activities (MedDRA) thesaurus levels and graded according to the National Cancer Institute Common Terminology Criteria for Adverse Events (NCI CTCAE) Version 4.0. AEs that occur during or after the first dose of study treatment (i.e., treatment-emergent adverse events [TEAEs]) will be included in the summary tables.

Adverse events will be summarized by MedDRA term, appropriate MedDRA levels (System Organ Class [SOC] and Preferred Term [PT]), and when specified by NCI CTCAE grade. For each patient, multiple occurrences of the same event will be counted once at the maximum severity.

The following adverse events will be summarized by SOC or medical concept for AEs of special interest (AESIs), PT, and NCI CTCAE grade, for each cohort:

- Adverse events (AEs)
- AEs and AESIs of Grade 3 or higher
- Adverse events related to i) any study treatment, ii) atezolizumab, iii) cobimetinib, iv) vemurafenib (Cohort 2 only), v) all study treatment.

- SAEs
- AESIs

The following AEs will be summarized by SOC or medical concept for AESIs and PT for each cohort:

- AEs
- SAEs
- AEs and SAEs related to i) any study treatment, ii) atezolizumab, iii) cobimetinib, iv) vemurafenib (Cohort 2 only), v) all study treatment.
- Adverse events leading to discontinuation of i) any study treatment, ii) atezolizumab, iii) cobimetinib, iv) vemurafenib (Cohort 2 only), v) all study treatment.
- Adverse events leading to dose modification or interruption of i) any study treatment, ii) atezolizumab, iii) cobimetinib, iv) vemurafenib (Cohort 2 only), v) all study treatment.
- AESIs specific to i) atezolizumab, ii) cobimetinib+vemurafenib, iii) the combination, based on lists of pre-defined terms.
- AESIs leading to discontinuation of i) atezolizumab, ii) cobimetinib, iii) vemurafenib
- AESIs leading to dose modification or interruption of i) atezolizumab, ii) cobimetinib, iii) vemurafenib
- Fatal AEs
- Serious AESIs

Adverse events will be summarized by PT for each cohort. In addition, deaths, SAEs, AESIs, and AEs during the run-in period and the triple combination period (i.e., post run-in), will be summarized for Cohort 2 only.

All listings of AEs will include all AEs. AEs associated with coronavirus disease (COVID-19) will be listed.

All deaths and causes of death will be summarized by cohort.

### **5.6.3 Laboratory Data**

Laboratory data will be summarized over time including change from baseline. Values outside the normal ranges will be summarized. Additionally, selected laboratory data will be classified in accordance with NCI CTCAE Version 4.0 and will be summarized by grade.

Highest NCI CTCAE grade post-baseline will also be reported, and shift tables from baseline to worst value during the study post-baseline will be presented.

Patient meeting the criteria for Hy's Law will be summarized.

#### **5.6.4 Vital Signs**

Actual values and changes from baseline in selected vital signs will be summarized over time.

#### **5.7 OTHER ANALYSES**

A shift table presenting the baseline ECOG performance status to worst post-baseline value will be provided by cohort.

A shift table presenting the baseline ECG assessment result to post-baseline value will be displayed by visit for the Cohort 2.

#### **5.7.1 Summaries of Conduct of Study**

Major protocol deviations, including violations of inclusion/exclusion criteria and deviations during study conduct, will be summarized by cohort.

All COVID-19 related major protocol deviations will be summarized by cohort.

#### **5.7.2 Summaries of Treatment Group Comparability/Demographics and Baseline Characteristics**

The following analyses will be based on the safety population.

Demographic characteristics such as age, sex, race/ethnicity, ECOG and other relevant baseline characteristics will be summarized by cohort. The disease baseline characteristics will include:

- Time since initial diagnosis (years)
- Primary diagnosis (Local regional, Metastasis, Unknown)
- Histologically confirmed sites
- Histological subtypes
- Initial diagnosis staging
- Time since initial diagnosis of metastatic melanoma (months)
- Stage at study entry
- BRAFV600 mutation status and type

Descriptive statistics (mean, median, standard deviation [SD], and range) will be presented for continuous data, and frequencies and percentages will be presented for categorical data.

The baseline value will be defined as the last available value recorded on or prior to the first administration of any study medication.

Prior cancer therapy, prior cancer radiotherapy, prior cancer surgery, follow-up cancer therapy, on-study radiotherapy, on-study targeted surgeries and procedures, follow-up

cancer radiotherapy, follow-up cancer therapy and follow-up cancer-related surgical procedures will be summarized by cohort. Previous and concurrent medical history, as well as medications, will also be summarized by cohort. In addition, the prior and concomitant anticonvulsants and systemic corticosteroid for disease control will also be summarized.

## **5.8 INTERIM ANALYSES**

### **5.8.1 Planned Interim Analyses**

A first safety interim analysis will be performed after at least 10 patients in each of both cohorts have completed their first tumor assessment (i.e., approximately eight weeks after start of study treatment). The analysis will be conducted by the Sponsor according to the Sponsor's standard operating procedures for safety reviews. The results of the interim analysis will be reviewed by the IMC as described in the IMC charter.

Full details on interim analyses are provided in the IMC charter.

### **5.8.2 Optional Interim Analyses**

Not applicable.

## **6. SUPPORTING DOCUMENTATION**

This section is not applicable, since there is no additional supporting document.

## **APPENDIX 1: CHANGES TO PROTOCOL-PLANNED ANALYSES**

The TTD for functional scale on QLQ-C30 is defined as 10 point of decrease from baseline instead of 10 point of increase as defined in the protocol. Indeed, a high score on functioning scale represent a high / healthy level of functioning as per the QLQ-C30 manual, thus an improvement.

The TTD analysis will be performed on the selected symptoms and functional scales for QLQ-C30 and BN20 separately since each item measures different level of functioning and symptomatology/problems.

